#### S.1 LAY SUMMARY

Anaemia due to low iron levels is common in older people and can cause tiredness and breathlessness. It is commonly treated with oral iron supplementation. However, oral iron supplementation does not improve anaemia in many people and they may have side effects. We do not know what strategy of care is best for patients who do not respond to oral iron supplementation: should we stop treatment, continue with supplementation (which is current practice) or switch to iron given by a drip (intravenous iron)?

We will conduct a pilot randomised controlled trial to identify what is the best way of finding and recruiting people who do not respond to oral iron supplementation, and to compare the three current strategies of care. We will recruit 84 older people with iron deficiency anaemia who are not improving on oral iron supplementation, and randomise them to receive one of the above three strategies of care for three months.

Key outcomes will include: how long it takes to recruit enough people to the study, which method(s) of recruitment (clinic, adverts or GP letters) is/are most efficient, and the improvement in haemoglobin level (a measure of anaemia) in each treatment arm.

The results will allow us to plan a large, multicentre trial to find out which of the three options should become routine clinical care in this situation.

#### S.2 SCIENTIFIC SUMMARY

Anaemia is a common problem, and is particularly common in older people. It is associated with fatigue, impaired functional capacity, increased hospitalization and mortality. In the USA, the prevalence of anaemia as defined by the World Health Organisation (Hb <130g/L in men and <120g/L in women) among community-dwelling adults age 65 years and older was 11.0% and 10.2% in men and women, respectively, rising to more than 20% in those >85 years.

In this pilot study we will recruit older people, aged 65 years or over, with mild-moderate iron deficiency anaemia (anaemia defined as haemoglobin (Hb) between 85 and 110 g/L and iron deficiency defined as ferritin <100µg/L prior to commencing oral iron) and who show insufficient response to oral iron therapy (sufficient response defined as improvement in Hb by 20g/L within 3 months of commencement of oral iron therapy) into a three-arm study. The study arms are:

- Treatment as usual
- Stop oral iron treatment
- Stop oral iron and give IV iron (as per local formulary).

The co-primary outcomes are:

- 1) the rate of randomisation per month across the pilot sites
- 2) the proportion recruited from each route of recruitment

Secondary outcomes are:

- 1) change in haemoglobin and ferritin levels at 3 months
- 2) number of eligible patients per site
- 3) proportion of eligible patients agreeing to take part and passing screening
- feasibility of collecting primary (physical functioning and health-related and general quality of life) and secondary outcomes for main trial:
  - Short physical performance battery
  - Six-minute walk distance
  - Anaemia-related symptoms (e.g. breathlessness, tiredness, fatigue)
  - Health-related quality of life (EQ-5D-5L™, 15D©)
  - Activities of daily living (NEADL©)
  - Health care use including use of blood transfusions and hospitalisation
  - All-cause mortality
- 5) dropout rate at 3 months; crossover rate at 3 months

- 6) reported side effects and adverse events (GI symptoms, headache, dizziness, rash)
- 7) functional limitation (six-minute walk <400m or short physical performance battery ≤10)
- 8) level of fatigue assessed using validated Fatigue Severity Scale
- 9) Patient experience.
- 10) Oral Iron Use Likert Scale (in those taking oral iron only)
- 11) Participant experience using semi-qualitative questionnaire.

#### Table 1: List of abbreviations

ADL	Activities of Daily Living				
AE	Adverse Event				
CI	Chief Investigator				
Co-Cl	Co-Chief Investigator				
CLRN	Comprehensive Local Research Network				
CRF	Case Report Form				
FSS	Fatigue Severity Scale				
GCP	Good Clinical Practice				
GP	General Practitioner				
HERA	Health Economics Research Unit (Aberdeen)				
HIC	Health Informatics Centre (Dundee)				
HRA	Health Research Authority				
ICF	Informed Consent Form				
IDA	Iron Deficiency Anaemia				
IMP	Investigational Medicinal Products				
ISF	Investigator Site File				
ITT	Intention To Treat				
IV	Intravenous				
NHS	National Health Service				
NIHR	National Institute for Health Research				
NRS	NHS Research Scotland				
PI	Principal Investigator				
PID	Personal Identifiable Data				
PIS	Participant/Patient Information Sheet				
RCT	Randomised Clinical Trial				
R&D	NHS Board/Trust R&D Department				
REC	Research Ethics Committee				
RN	Research Nurse				
SAE	Serious Adverse Event				
PCN	Primary Care Network				
SmPC	Summary of Product Characteristics				
SOP	Standard Operating Procedure				
SPPB	Short Physical Performance Battery				
TASC	TAyside Medical Science Centre				
TCTU	Tayside Clinical Trials Unit				
TMF	Trial Master File				
TMG	Trial Management Group				

#### 1 INTRODUCTION

#### 1.1 BACKGROUND

Anaemia is a common problem and is particularly common in older people. It is associated with fatigue, impaired functional capacity, increased hospitalisation and mortality (1) In the USA the prevalence of anaemia as defined by the World Health Organisation (Hb <130g/L in men and <120g/L in women) (2) among community-dwelling adults age 65 years and older was 11.0% and 10.2% in men and women, respectively (3), rising to more than 20% in those >85 years (4).

Iron deficiency is one of the commonest causes of anaemia. It can be diagnosed by the presence of low ferritin levels or low serum iron and transferrin saturation levels (5). The estimated prevalence of iron deficiency anaemia (IDA) in adult men and post-menopausal women in western countries is 2-5% (5). IDA is especially common in older people (6); it accounts for up to 30% of all cases of anaemia in older adults (7). In Tayside, Scotland, alone approximately 5,000 people over the age of 65 (i.e. ~5% of the population in this age group) received at least one prescription for oral iron in the year 2015-2016. Large numbers of people in Scotland are therefore treated for iron deficiency, many of whom are on long term treatment, making the question of how to treat this condition most effectively an important one for patients, clinicians and healthcare funders.

Despite the widespread use of oral iron to treat even mild IDA in older people, evidence is lacking on the best way to treat this condition, or indeed whether treatment is required at all in mild cases. Our recent systematic review found only three RCTs testing the efficacy of oral iron compared to placebo or no iron. The treatment effect was trivial: haemoglobin levels increased by a mean of only 3.5g/L (95%CI:1.2-5.9g/L) (8). Routinely collected data from older people in Tayside support these findings with most recipients of oral iron showing little or no improvement in haemoglobin levels; many older patients are exposed to oral iron without good evidence of a significant response to therapy (9).

A further problem with the existing evidence is that the available trials did not aim to measure outcomes relevant to older patients – such as symptom improvement or improvement in physical performance, activities of daily living or quality of life (7). Furthermore, a review of the evidence for intravenous iron found no precise comparison of the clinical benefit of different iron preparations (10).

Current practice is to treat older people with iron-deficiency anaemia with oral iron after relevant investigations and management of any treatable causes. Oral iron therapy is aimed at correcting the

[figure not shown]

deficiency and also to replenish iron storage (11). One reason why oral iron may be ineffective at improving anaemia in many older people is due to the coexistence of other diseases, particularly chronic inflammation and chronic kidney disease. Hepcidin regulates entry of iron into circulation and high hepcidin levels are seen in chronic inflammation. These in combination affect hepcidin pathways with resultant reduction in iron absorption from gut mucosa (6). A second important reason why oral iron may be ineffective relates to the fact that it causes side effects in up to 40% of people - particularly gastrointestinal symptoms (12) with subsequent impact on diet, nutrition and health related quality of life (13, 14). Oral iron is consequently poorly adhered to and thus compliance is an issue with long term therapy. Intravenous iron can overcome both of these problems, but it is more expensive than oral iron and carries a small, but non-trivial risk of anaphylactoid reactions.

Despite this, analysis of routinely collected data from older patients who had undergone inpatient rehabilitation between 1999 and 2011 showed oral iron treatment non-systematic, and lack clear clinical pathways in real world setting (9). In this study (Thomson, Hands and Witham) we found that a total of 490 patients were prescribed oral iron within 90 days of rehabilitation discharge. Of these, 413 (84%) had iron indices performed; 94 (23%) were possibly deficient (transferrin 2.0-2.5g/L, ferritin 50-100µg/L), 224 (54%) were probably deficient (>2.5g/L and <50µg/L), and 95 (23%) were not deficient (>2.0g/L and >100µg/L). Of the 490 patients, 360 had both pre- and post-treatment haemoglobin data and iron indices; neither probably deficient nor possibly deficient patients showed a large improvement in haemoglobin levels, although probably deficient patients mounted a slightly greater response to oral iron (17 vs. 12 g/L for not deficient; p < 0.05). This finding of only a weak rise in Hb in this cohort further strengthened the evidence that many older patients are exposed to oral iron without good evidence of a significant response to therapy.

#### 1.2 RATIONALE FOR THE STUDY

A satisfactory response (rise in Hb of 20g/L) to oral iron is usually expected within 6-8 weeks of commencing treatment. The current standard of care is to continue oral iron even if a suboptimal (or no) response is seen. It is unclear if the current standard of care is of value to patients and healthcare providers. The balance of benefit and harm for oral iron in older people is unclear, and the best strategy for those not responding to oral iron is also unclear. Should oral iron be continued for longer, switched to intravenous iron, or simply stopped if it is not working? It is also uncertain whether further oral or IV iron therapy improves physical function and quality of life compared to no therapy in older patients with iron-deficiency anaemia.

We conducted an online survey of geriatricians and GPs in November 2016 through the British Geriatrics Society. Our survey confirmed the uncertainties in managing IDA, evident by inconsistent approaches and lack of clinicians' knowledge on whether the choice of management actually improved patient outcome. Over 85% of respondents stated that they regularly prescribe oral iron in at least 50% of their patients with IDA. 30% of respondents regularly prescribe oral iron in almost all of their patients with IDA. Although >85% who responded were willing to facilitate recruitment of eligible patients into a trial, they indicated some reluctance to discontinue oral iron therapy. Therefore, the proposed trial design needs a pilot study to demonstrate if recruitment is feasible.

We have run focus groups with older people who have IDA and received either oral or IV iron. They identified being symptom-free with improved quality of life and the ability to carry out daily tasks as the most desirable outcomes for therapy. They suggested that potential participants would be willing to receive an invitation letter to participate in the proposed study either from their own GP or their hospital consultant. They were uncertain about the idea of continuing oral iron if it had been ineffective, despite this being current standard practice. No ethical issues or concerns have been raised by clinicians or patients. However, we are aware of potential side effects of IV iron administration and therefore safety outcomes have been included as one of the secondary outcomes in this pilot.

This pilot study is a critical step towards a definitive multicentre trial, which we would plan to submit to the NIHR HTA programme for funding. The definitive multicentre trial would provide the evidence of clinical effectiveness using outcomes most relevant to older people (physical function and quality of life, rather than just relying on haemoglobin measurements) and importantly, of cost-effectiveness – a particular issue with the increasing use of IV iron, which is relatively expensive compared to oral iron.

## 2 STUDY OBJECTIVES & OUTCOMES

A summary of study objectives and outcomes is provided in Table 2 and Table 3

#### **Table 2: Primary Objectives and Outcome Measures**

Primary Objective:	Outcome Measure:	Timepoint of outcome measured:
To estimate the recruitment rates and	The rate of randomisation per month across all pilot sites.	End of recruitment / End of study.
examine recruitment strategies at pilot sites across different settings and different NHS	The proportion recruited from each route of recruitment which include (i) primary care and secondary care prescription; (ii) blood test results;	End of recruitment / End of study.
providers.	
 
(iii) through individual clinicians;
 
(iv) from public
 
advertisement;
 
and
 
(v) SHARE database.
 
	

#### **Table 3: Secondary Objectives and Outcome Measures**

Secondary Objective:	Outcome Measure:	Timepoint of outcome measured:
To examine the change in a key surrogate outcome (haemoglobin levels).	n a key surrogate months. outcome (haemoglobin	
To examine the change in secondary surrogate outcome.	secondary surrogate	
To obtain preliminary	Number of eligible patients per site	0 & 3 months.
data on the proposed patient outcomes	Proportion of eligible patients agreeing to take part and passing screening.	
(quality of life, symptoms and physical	Feasibility of collecting proposed outcomes for a future definitive trial:	
function).	Short physical performance battery (SPPB) (15)	
	Six-minute walk distance	
	Anaemia-related symptoms	
	Health-related quality of life (EQ-5D-5L ™ , 15D©) (16) (17)	
	Activities of daily living (NEADL©) (18)	
	Functional limitation (using 6 minute walk & SPPB)	
	Fatigue Severity Scale (19)	
	Oral Iron Use Likert Scale (oral iron only).	
	Health care use	3 months.
	All-cause mortality	
	Dropout rate at 3 months	
	Crossover rate at 3 months	
	Participant experience semi-qualitative questionnaire.	

#### 2.1 OBJECTIVES

#### 2.1.1 Primary Objectives

The primary objective of this pilot study is to estimate the recruitment rates and examine recruitment strategies at pilot sites across different settings and different NHS providers.

#### 2.1.2 Secondary Objectives

The secondary objectives are to examine the change in a key surrogate outcome (haemoglobin and ferritin levels) and to obtain preliminary data on the proposed patient outcomes (quality of life, symptoms and physical function) to inform the sample size calculation for a future definitive trial.

#### 2.2 OUTCOMES

#### 2.2.1 Co-Primary Outcomes

- 1) The rate of randomisation per month across all pilot sites
- 2) The proportion recruited from each route of recruitment which include:
  - primary care and secondary care oral iron prescriptions
  - NHS electronic blood test results
  - through individual NHS clinicians and GPs
  - from public advertisement and press releases
  - research volunteer databases, including SHARE.

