#### 5.1.3 Recruitment Strategies

#### (i) Primary and secondary care prescriptions

To identify potentially eligible participants, oral iron prescription searches will be performed by Primary Care Network, GPs and/or hospital clinicians.

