#### (ii) Laboratory results lists

To identify potentially eligible participants, biochemistry and haematology results listings will be created by the NHS laboratory at each site. Haemoglobin results will be reviewed by GPs/hospital clinicians or delegated.

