#### **GP** Practice lists

Potential participants will be identified via the NHS Research Scotland Primary Care Network (NRSPCN) and NIHR Primary Care Network as follows:

• Research active general practices in the NRS / NIHR PCN will be invited to join the study.

Recruitment of patients from the primary care by NRS & NIHR Primary Care Network
 The NRSPCN (previously called SPCRN) / NIHRPCN will be involved in recruitment of patients
 to this study from primary care. Network staff provide GP practices with an expert service to

undertake searches of their electronic databases to identify potentially eligible patients and prepare the ethically approved letters to be sent out by the practice. Network staff work on behalf of the healthcare team under practice staff supervision. Each member of Network staff must have a current NHS substantive or honorary contract in order to carry out these activities. Searches are undertaken of each GP practice database and the list generated by the search is screened by a clinician before the letters are sent out on behalf of the practice. Patients are asked to contact the research team if they are interested in participating in the study.

- Using the practice IT system and the Community Health Index (CHI) number (a unique NHS Scotland patient identifier) / relevant identifier a search of patients receiving oral iron treatment will be carried out to establish potential eligibility will be carried out to identify potentially eligible participants;.
- The GP will write to eligible patients using the Invitation Letter, providing the brief Participant Information Brochure, and inviting those interested in taking part to reply using the reply slip and stamped addressed envelope or to call or e-mail the study team.

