#### 5.1.4 Invitation Mailings

All invitation packs will be sent via HIC. HIC is a University of Dundee research support unit within the Tayside Medical Science Centre (TASC). All services provided by HIC are delivered within an ISO 270001 certified secure environment to ensure data is managed safely and in compliance with Data Protection legislation. The identified invitation lists will be stored securely within the NHS network. The invitation pack will consist of an invitation letter with a

reply slip, brief information sheet/leaflet and pre-paid return envelope. The research team will not have access to this confidential invitation list. HIC will also send any reminders with the relevant PIS.

Participants can indicate their interest in the study by completing and returning the reply slip using the pre-paid envelope or by calling/e-mailing the study team. Those interested will be sent information sheet. HIC will upload all positive replies allowing the relevant study team access contact details of the potential participant. These details are uploaded onto the secure web based Recruitment Tracker. The Cohort ID generated during the invitation stage will be used the participant identifier. For participants who state they do not wish to be contacted, their details will be not be uploaded and they will not receive any further communication. These details are not visible to the study team.

If required, a reminder letter will be sent to participants.

Participants who independently contact the study team having seen study information i.e. poster / advertising, the local team will upload the contact details onto the PMS, thereafter HIC will be send the invitation pack.

The Recruitment Tracker will document each positive response and with consent participant contact details allowing the study team to efficiently communicate with participants, GPs and secondary care physicians.

For data management purposes, identifiable information, completed consent forms and anonymised study data will be securely stored in locked cupboards, password protected databases and spreadsheets in the University of Dundee. Identifiable information will be stored separately from study data. Authorised members of the trial and data management team will have access to identifiable information to allow the management of study visits.

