#### 9.2 STATISTICAL ANALYSIS PLAN

All analyses will be by intention to treat, and will thus include all participants randomised. Data will be analysed by an independent statistician from Medical Statistics Team and a Research Assistant from HERU.

Baseline demographics and clinical characteristics will be presented as mean (SD), median (IQR) or percentage (n) as appropriate across study arms. Hb and ferritin level at 3 months will be compared across study arms using analysis of covariance with baseline Hb and ferritin level and site as covariates. Intra study arm comparisons will be assessed using the paired t-test or Wilcoxon signed rank test. Number of eligible patients per site, recruitment rate across sites, the proportions recruited by each method within site, dropout and crossover rates, all with corresponding 95% confidence intervals will each be tabulated. Effect size estimates of difference in Hb and ferritin level between arms will be calculated. The latest available SPSS version at the time of conducting statistical analysis will be used for analysis with intention to treat as the main analysis.

A per-protocol analysis will also be performed on completers of the study as a secondary analysis, primarily for safety outcomes (adverse event rates, falls).

Health economic measures (costs of healthcare use, comprising hospital stays for reasons related to

anaemia and outpatient/day case visits for iv iron administration, costs of blood transfusion and oral iron, and quality of life measurement using EQ-5D-5L and 15D) will be presented as unadjusted mean (SD) and median (IQR) values. Regression-based adjusted costs and quality of life values will also be calculated, with baseline cost, quality of life values, treatment group and patient demographics as co-variates. The percentage of missing data per resource use item and per quality of life questionnaire will also be presented.

We will assess both feasibility of secondary outcome measures and distribution of changes; these data will form the basis for sample size calculations for the full trial.

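### Co-primary outcome 2 is counted over overlapping recruitment routes with no assignment rule, and approach counts are not tied to route, so it shows contribution and not efficiency

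*Protocol*

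**What the plan says.** The primary objective (section 2.1.1) is "to estimate the recruitment rates and examine recruitment strategies at pilot sites across different settings and different NHS providers". The lay summary (S.1) lists among the key outcomes "which method(s) of recruitment (clinic, adverts or GP letters) is/are most efficient". The second co-primary outcome (section 2.2.1, also Table 2) is "The proportion recruited from each route of recruitment which include" prescriptions, blood test results, clinicians and GPs, advertising, and volunteer databases. Section 9.2 tabulates "the proportions recruited by each method within site" with 95% confidence intervals. None of these places states the denominator.

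Section 5.1.3 describes how each route works:

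- Route (i): "oral iron prescription searches will be performed by Primary Care Network, GPs and/or hospital clinicians".
- Route (ii): the laboratory produces listings, and "Haemoglobin results will be reviewed by GPs/hospital clinicians or delegated".
- Route (iii), GP practice lists: the primary care network works on the practice system, where "a search of patients receiving oral iron treatment will be carried out to establish potential eligibility". Under hospital clinics, clinical teams review their patients on oral iron.
- Route (v): volunteer databases are also searched for people on oral iron.

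On data capture, section 5.2 takes recruitment source from the patient management system. Section 5.3 logs notes reviewed, people pre-screened and screened, and reasons for ineligibility, and calls these co-primary outcome data. Section 5.1.4 sends every invitation pack through one central unit and adds: "The research team will not have access to this confidential invitation list".

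**The concern.** There are two separate weaknesses.

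First, the categories are not mutually exclusive. Routes (i) and (iii) can be the same search, by the same network, on the same database. Because current oral iron is an inclusion criterion (section 4.2), every eligible patient could in principle appear on a prescription list as well as on a laboratory or clinic list. Without a rule, the route recorded for such a person depends on who fills in the field.

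Second, the measure and the question differ. On its natural reading, the proportion recruited from a route is that route's share of all recruits. A share rises with the number of people approached through the route. Efficiency needs the number approached or screened by that route, and the protocol does not say that those counts are split by route.

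This is one of only two co-primary outcomes, and section 5.1.1 says that the sites were selected to establish the recruitment plan for the main study. A ranking of routes that reflects mailing volume and coding habit would be a poor basis for that plan. If the counts are not captured by route while recruitment runs, a later analysis plan may be unable to recover them.

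**Working it through.** **The plan's own figures.** The protocol states no expected value for this outcome. The number randomised is 84: 4 sites × 3 arms × 7 = 84 (section 4.1). From 60 completers and 30% dropout (section 9.1), 60 / (1 − 0.30) = 85.7, or 86 rounded up, within two of the stated 84. Nothing here changes that number. It serves below as the denominator of a share.

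**Check 1: do the routes overlap?** Set side by side, route (i) is an oral-iron prescription search by the network, GPs or hospital clinicians; route (iii) includes a practice-system search for patients on oral iron by the network. One search satisfies both descriptions. The labels also move. Route (iii) is individual clinicians in Table 2 and section 2.2.1, but patient lists including GP databases in section 5.1.2. The lay summary has three methods, and its GP letters could belong to (i), (ii) or (iii). No section ranks the routes or says that the first contact counts.

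**Check 2: how much could coding move a share?** Assumption, not in the documents: k of the 84 qualify under two routes, and the other 84 − k split equally over five routes. One route's share then runs from [(84 − k)/5]/84 to [(84 − k)/5 + k]/84.

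| Overlap | k | Lowest share | Highest share |
|---|---|---|---|
| 10% | 8 | 15.2/84 = 18% | 23.2/84 = 28% |
| 25% | 21 | 12.6/84 = 15% | 33.6/84 = 40% |
| 50% | 42 | 8.4/84 = 10% | 50.4/84 = 60% |

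The width of the range is simply the assumed overlap. For comparison, the sampling uncertainty of a 20% share (17/84) is 13% to 30% (Wilson 95% interval). At 25% overlap, the coding range is wider than that interval.

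**Check 3: can share and yield rank routes differently?** Illustration with assumed approach counts:

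- Prescription-based letters: 42 randomised from 2,000 letters. Share 42/84 = 50%; yield 42/2,000 = 2.1% (95% CI 1.6 to 2.8).
- Clinician approaches: 12 randomised from 60. Share 12/84 = 14%; yield 12/60 = 20% (95% CI 11.8 to 31.8).

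The order reverses. This shows only that the two measures can disagree; it predicts nothing about this trial.

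**Check 4: are the ingredients for a yield collected?** Source: yes (section 5.2). Notes reviewed, pre-screened and screened: yes (section 5.3), but not stated by route. Invitations: countable, because one unit sends them all (section 5.1.4), but no return of counts by route is stated.

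**The case against.** The strongest reply is that the protocol already holds most of what is needed. Source is recorded, screening activity is logged monthly as co-primary data, mailing is central, and section 8.2 says that the tracker is designed to report the co-primary outcomes. A coding hierarchy and table denominators often sit in an analysis plan or data management plan, and neither is shown. A route's contribution is also a legitimate descriptive outcome for a pilot, and the word efficient appears in the lay summary, not in the formal objective.

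Much of this stands, and it rules out several stronger readings:

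- A reader might infer that the trial cannot show which route is efficient. It could, if the counts in section 5.3 and the mailing counts are kept by route. The gap is that the protocol does not say they are.
- A reader might infer from the confidential invitation list that acceptance is observable only among people who replied positively. Sections 5.1.4 and 5.1.4.1 withhold identifiable details; they do not bar aggregate counts. Notes reviewed (section 5.3) are not limited to repliers.
- A reader might object to tabulating within site, where 4/21 has a 95% interval of 8% to 40%. But the objective concerns strategies across settings and providers, wide intervals are expected in a pilot, and pooled counts are the sum of the site rows.
- A reader might say that the outcome has no denominator at all. A share of those randomised would have one, namely 84. The text leaves the choice open; what is missing is the number approached by route.

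The reply does not resolve the overlap between (i) and (iii), which is in the protocol's own definitions. Nor does it help to defer counts by route to a document written after recruitment.

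**Conclusion.** The point holds in limited form. The routes of co-primary outcome 2 overlap, no rule assigns a person found by more than one, and screening and invitation counts are not tied to route. As defined, the outcome measures contribution to recruitment, not the efficiency that the lay summary promises.

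The size cannot be fixed from the protocol. It depends on how many participants are findable by two routes and on how many people are approached through each, and neither figure is given; the ranges above rest on assumed values. The conclusion also assumes that the proportion recruited means a share of recruits, which is the natural reading but is not stated.

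This should be settled before recruitment because it concerns data capture. It is not a critical flaw: the randomisation rate, the sample size, the safety data and the comparisons between arms do not depend on it.

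**What to change.** 1. **One exclusive source per participant**: the list or contact that first triggered the approach. Code GP, network and hospital prescription-database searches to (i), and keep laboratory listings in (ii). Reserve (iii) for patients identified individually by a clinician, and leave volunteer-database searches in (v) even though they also look for people on oral iron. Use the same labels in S.1, Table 2 and sections 2.2.1, 5.1.2 and 5.1.3.
2. **Counts by route**: keep the section 5.3 screening counts by route. Have the mailing unit return aggregate numbers of packs sent, replies and declines by site and route, without identifiable data.
3. **Report two measures per route**, pooled and by site, with 95% confidence intervals: share = randomised by route / all randomised; yield = randomised by route / approached by route.
4. **Treat advertising separately**: its packs go out only after a person has made contact (section 5.1.4), so a yield per pack would flatter it. Report yield per enquiry and do not compare it directly with the mailed routes.

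The cost is one source field, a routine aggregate count from a unit that already sends every pack, and a wording change in the protocol.
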